### **3.1.3. Vital Signs**

Single supine blood pressure and pulse measurements will be taken at times detailed in the SoA given in the protocol.

Baseline will be defined as the last pre-dose measurement.

The following vital signs endpoints will be determined:

- Change from baseline in supine systolic and diastolic blood pressure, pulse rate, temperature and respiratory rate.
- The maximum decrease from baseline over all measurements taken post-dose for supine systolic and diastolic blood pressures and respiratory rate.
- The maximum increase from baseline over all measurements taken post-dose for supine pulse rate and temperature.

The maximum increase from baseline will be calculated by first subtracting the baseline value from each post-dose measurement (both planned and unplanned) to give the change from baseline. The maximum of these values over the respective period will then be selected, except in the case where a participant does not show an increase. In such an instance, the minimum decrease should be taken.

Similarly, the maximum decrease from baseline will be determined by selecting the minimum value of the changes from baseline. In cases where a participant does not show a decrease, the minimum increase should be taken.

### **3.1.4. ECG**

Only centrally read ECG data will be used.

A single 12-lead ECG will be obtained on all participants at screening.

12-lead ECGs will be recorded in triplicate on all subjects at times detailed in the SoA given in the protocol. The QT, heart rate, QTcF, PR and QRS will be recorded at each assessment time.

The average of the triplicate readings collected at each assessment time will be calculated for each ECG parameter. Baseline will be defined as the average (if possible) of the triplicate pre-dose recordings on Day 1.

The following ECG endpoints will be determined:

- Change from baseline in QT interval, heart rate, QTcF interval, PR interval, and QRS complex.
- The maximum absolute value (post-dose) will be calculated for QTcF, PR and QRS
- The maximum increase from baseline over all measurements taken post-dose will be calculated for QTcF.

The maximum increase from baseline will be calculated by first subtracting the baseline value from each post-dose measurement (both planned and unplanned) to give the change from baseline. The maximum of these values over the respective period will then be selected, except in the case where a participant does not show an increase. In such an instance, the minimum decrease should be taken.

### **3.1.5. Pulse Oximetry/SpO2**

Pulse oximetry/SpO2 will be taken at times detailed in the SoA given in the protocol.

The following pulse oximetry endpoints will be determined:

- Change from baseline in pulse oximetry/SpO2

Baseline will be defined as the last pre-dose measurement.

## **3.2. Secondary Endpoint(s)**

Blood samples for PK analysis of PF-07304814 and PF-00835231 will be taken according to the SoA given in the protocol. Urine PK was only planned to be collected in Part 1: SAD Cohort 2 and as this was not conducted, has been removed from the SAP.

Plasma PK parameters of PF-07304814 and PF-00835231 will be derived (if data permit) from the concentration-time data using standard noncompartmental methods following 24h infusion (see Table 2) or 120h (see Table 3) infusions. .

**Table 2. Noncompartmental PK Parameters for Part 1: SAD**

| Parameter     | SAD Dose   | Analysis Scale | PF-07304814 | PF-00835231 |
|---------------|------------|----------------|-------------|-------------|
| $AUC_{last}$  | 500mg only | ln             | D           | D           |
| $AUC_{inf}^*$ | 500mg only | ln             | D           | D           |
| $C_{24}$      | All        | ln             | D           | D           |
| $C_{ss}$      | 500mg only | ln             | D           | D           |
| $C_{max}$     | 500mg only | ln             | D           | D           |
| $t_{1/2}^*$   | 500mg only | R              | D           | D           |
| $CL^*$        | 500mg only | ln             | D           |             |
| $V_{ss}^*$    | 500mg only | ln             | D           |             |

Key: D=displayed with descriptive statistics,  
 ln=natural-log transformed, R=raw (untransformed),  
 \*=if data permits, dn = normalized to a 1mg PF-07304814 dose

**Table 3. Noncompartmental PK Parameters for Part 2: MAD**

| Parameter      | Analysis Scale | PF-07304814 | PF-00835231 |
|----------------|----------------|-------------|-------------|
| $C_{120}$      | ln             | D           | D           |
| $C_{max}$      | ln             | D           | D           |
| $C_{ss}$       | ln             | D           | D           |
| $T_{max}$      | R              | D           | D           |
| $t_{1/2}^*$    | R              | D           | D           |
| $C_{120}$ (dn) | ln             | D           | D           |
| $C_{ss}$ (dn)  | ln             | D           | D           |

Key: D=displayed with descriptive statistics,  
 ln=natural-log transformed, R=raw (untransformed),  
 \*=if data permits, dn = normalized to a 1mg PF-07304814 dose

### 3.3. Other Endpoint(s)

#### 3.3.1. SARS-CoV-2 Viral Load

Nasopharyngeal swab and saliva samples will be collected according to the SoA given in the protocol.

Baseline will be the last pre-dose measurement.

The following viral load endpoints will be determined and reported as separate endpoints:

- Change from baseline in nasopharyngeal swab and saliva viral load

#### 3.3.2. Biomarkers

Exploratory biomarkers will be collected according to the SoA given in the protocol.

Baseline will be the last pre-dose measurement.

The following biomarker endpoints will be determined:

- Change from baseline in blood hs-CRP, LDH, Ferritin, WBC, Monocytes, Haptoglobin, Procalcitonin, Neutrophils and Creatine Kinase
- Change from baseline in coagulation markers D-dimer, PT, aPTT and Fibrinogen
- Change from baseline in cytokines of inflammatory response

Reactive and Non-Reactive IgG will be collected according to the SoA given in the protocol.

All other exploratory biomarkers will be used for internal exploratory purposes and will not be included in the CSR but reported in a separate addendum.

CCI

CCI

### 3.4. Baseline Variables

N/A.

### 3.5. Safety Endpoints

See [Section 3.1](#) for details.

## 4. ANALYSIS SETS (POPULATIONS FOR ANALYSIS)

Data for all participants will be assessed to determine if participants meet the criteria for inclusion in each analysis population prior to unblinding and releasing the database and classifications will be documented per standard operating procedures.

| Population  | Description   |
|---|---|
| Enrolled/Randomly assigned to study intervention | "Enrolled" means a participant's, or his/her legally authorized representative's, agreement to participate in a clinical study following completion of the informed consent process. Potential participants who are screened for the purpose of determining eligibility for the study, but do not participate in the study, are not considered enrolled, unless otherwise specified by the protocol. |
| Evaluable  | All participants randomly assigned to study intervention and who take at least 1 dose of study intervention for the given part of the study (Part 1: SAD or Part 2: MAD).   |
| Safety   | All participants randomly assigned to study intervention and who take at least 1 dose of study intervention for the given part of the study (Part 1: SAD or Part 2: MAD). Participants will be analyzed according to the product they actually received.  |
| PK Concentration Set                             | All participants randomly assigned to study intervention and who take at least 1 dose of study intervention and in whom at least 1 concentration value is reported for the given part of the study (Part 1: SAD or Part 2: MAD).  |
| PK Parameter Set                                 | All participants randomly assigned to study intervention and who take at least 1 dose of study intervention and in whom at least 1 of the PK parameters of interest are reported for the given part of the study (Part 1: SAD or Part 2: MAD).  |
| Biomarker Analysis Set                           | All participants randomly assigned to study intervention and who take at least 1 dose of study intervention and in whom at least 1 of the biomarkers of interest are reported for the given part of the study (Part 1: SAD or Part 2: MAD).   |

## **5. GENERAL METHODOLOGY AND CONVENTIONS**

### **5.1. Hypotheses and Decision Rules**

There is no statistical hypothesis testing planned for this study and no statistical decision rules will be applied.

### **5.2. General Methods**

Unless otherwise stated, all summaries and plots will be presented by treatment. Screening and Early Termination will be included in the summaries.

#### **5.2.1. Analyses for Continuous Endpoints**

Continuous variables will be presented using summary statistics: number of observations, arithmetic mean, standard deviation, median, minimum and maximum values.

Log transformed continuous variables will be presented using summary statistics: number of observations, arithmetic mean, median, cv%, standard deviation, minimum, maximum, geometric mean and geometric cv%.

#### **5.2.2. Analyses for Categorical Endpoints**

Categorical variables will be presented using summary statistics: number of observations and percentages.

### **5.3. Methods to Manage Missing Data**

For the analysis of safety endpoints, the sponsor data standard rules for imputation will be applied.

In all PK data presentations (except listings), concentrations below the limit of quantification (BLQ) will be set to zero.

In listings, BLQ values will be reported as “<LLQ”, where LLQ will be replaced with the value for the lower limit of quantification (LLQ).

For PK summary tables and plots of mean/median profiles, statistics will be calculated having set concentrations to missing if 1 of the following cases is true:

1. A concentration has been collected as ND (ie not done) or NS (ie no sample),
2. A deviation in sampling time is of sufficient concern or a concentration has been flagged anomalous by the pharmacokineticist/statistician.

For listing of viral load and cytokine data, BLQ values will be reported as “<LLQ”, where LLQ will be replaced with the value for the lower limit of quantification (LLQ). For summaries and plots BLQ values will be replaced with the value for the lower limit of quantification (LLQ).

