Maximum or near maximum plasma concentrations of the active moiety PF-00835231 were generally first observed ~6h post start of the infusion and sustained until the end of the infusion. PF-00835231 plasma concentrations declined rapidly afterwards. The $t_{1/2}$ values were only reportable at 500 and 700 mg and were 2.25 hour and 2.02 hour, respectively. Mean C_{max} and AUC values appeared to increase in a dose proportional manner in the dose range tested.

Maximum or near maximum plasma concentrations of the phosphate prodrug PF-07304814 were generally first observed ~3h and sustained until at least 16h post start of the infusion. Despite continuous infusion of the prodrug and sustained plasma concentration of the active moiety, the concentration of PF-07304814 declined before the end of the infusion. The $t_{1/2}$ values could not be determined since all plasma samples collected after the 16h post start of the infusion were BLQs of 40 ng/mL. While the mean C_{max} values appeared to increase in a dose proportional manner in the dose range tested, the AUC values appeared to increase in a slightly greater than dose proportional manner.

More detailed information may be found in the latest IB (December, 2020).

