4.3.2. Starting Dose and Dose Escalation in Part 1: SAD

This is a study in COVID-19 patients who are on SoC. To maximize the potential benefit of an anti-viral agent, the planned starting dose of PF-07304814 is to maintain a free plasma concentrations (C_{ss}) of PF-00835231 (active moiety) around EC₉₀ of 0.5 μM (or a total plasma concentration of 0.526 μg/mL) according to in vitro pharmacology studies ([Section 2.2.1.2.2](#)).

Based on the predicted human PK parameters (Section 2.2.1.2.1), at a dose of 500 mg of PF-07304814 administered over 24-hour as a continuous infusion, the projected PF-00835231 (active moiety) C_{ss} is 0.53 $\mu\text{g}/\text{mL}$ and the AUC_{24} is 11.2 $\mu\text{g}\cdot\text{h}/\text{mL}$. CCI

[REDACTED] (Section 2.2.1.3). At this dose, the projected PF-07304814 exposures (C_{ss} and AUC_{24}) provide at least 2.5-fold safety margins relative to the PK stopping limits (Section 2.2.1.3).

As of 18 November 2020, 4 patient participants received a single dose of 500 mg PF-07304814 or placebo administered as a 24-hour continuous IV infusion in study C4611001. While the preliminary safety profiles were acceptable, the exposures achieved at 500 mg in C4611001 were ~2-fold of initial PK stopping limits based on preliminary results in a limited number of patients who received active treatment. As such, the enrolment to Cohort 1 at 500 mg was stopped and a new cohort (Cohort 3) at 250 mg is open to enrolment.

If dose progression is further explored in Part 1 of the study, the predicted exposures for both PF-00835231 and PF-07304814 will not exceed the agreed PK stopping limit with competent regulatory authorities.

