4.3.3. Starting Dose and Dose Selection in Part 2: MAD

The starting dose of Part 2 is determined to be 5 daily doses of 250 mg via continuous infusion after careful review of all available safety and PK data from Part 1: SAD of study C4611001 as well as data from study C4611007. This starting dose has been selected to balance the safety of trial participants while maintaining the $C_{ss} > EC_{90}$ through the entire dosing interval and is intended not to exceed the initial PK stopping limits, CCI [REDACTED] (Table 5).

Emerging PK data from those who received active treatment of 500 mg in Part 1 suggest that the exposures (C_{max} and AUC) of the active moiety PF-00835231 were roughly 2-fold (AUC_{24}) to 3-fold (C_{max}) higher compared to those observed in healthy participants (C4611007) based on geometric mean values. The $t_{1/2}$ was similar to those in healthy participants when values could be calculated.

Because of the anticipated higher exposure in the patient population as compared to healthy participants and the variability in patients observed so far, 250 mg daily for 5 days dosing regimen will enhance the probability of maintaining the $C_{ss} > EC_{90}$ for patients enrolled. Therefore, this starting dosing regimen will balance achieving antiviral activity while remaining within the initial PK stopping limits CCI [REDACTED]

If the 250 mg daily for 5 days dosing regimen is safe and well tolerated, further dose escalation will be guided by safety as well as PK of the drug. The escalation increment, if explored will be $\leq 2.5X$ (eg, from 250 mg to ≤ 625 mg). Two optional cohorts may be added to explore higher doses or to repeat a dose to expand the cohort. Dose escalation will only proceed after gaining agreement on the dose level from competent regulatory authorities.

Furthermore, dose escalations will be undertaken in a cautious manner such that systemic exposures of PF-00835231 and PF-07304814 at any dose level in Part 2 will not exceed exposure observed from mid-dose of CCI [REDACTED] (Section 2.2.1.3).

Projected PK exposure parameters and safety margins of PF-00835231 and PF-07304814 relative to exposure limits for **Part 2** based on initial PK stopping limits at the planned dose are listed in Table 5 and Table 6, respectively. Doses presented are projected based on preliminary PK results from study C4611007.

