9.4.2. Secondary Endpoint: Pharmacokinetic Analyses

9.4.2.1. Derivation of Pharmacokinetic Parameters

Plasma PK parameters of PF-07304814 and PF-00835231 to be derived (if data permit) from the concentration-time data using standard noncompartmental methods following 24h or 120h infusion are defined in Table 7 and Table 8, respectively. Urine PF-00835231 PK parameters following 24h infusion are defined in [Table 9](#).

Actual PK sampling times will be used in the derivation of PK parameters. In the case that actual PK sampling times are not available, nominal PK sampling time will be used in the derivation of PK parameters.

Table 7. Plasma PF-07304814 and PF-00835231 PK Parameters Definitions for Part 1: SAD (24-h Continuous Infusion)

Parameter	Definition	Method of Determination
C_{24}	Concentration at 24h (end of infusion in Part 1)	Observed directly from data
$C_{24}(\text{dn})$	Dose normalized C_{24}	C_{24}/Dose

Actual PK sampling times will be used in derivation of PK parameters.

Table 8. Plasma PF-07304814 and PF-00835231 PK Parameters for Part 2: MAD (120-h Continuous Infusion)

Parameter	Definition	Method of Determination
C_{120}	Concentration at 120h (end of infusion)	Observed directly from data
C_{max}	Maximum observed concentration	Observed directly from data
C_{ss}	Steady state concentration	Average concentration after achieving steady state
$t_{1/2}^*$	Terminal half-life.	$\text{Log}_e(2)/k_{\text{el}}$, where k_{el} is the terminal phase rate constant calculated by a linear regression of the loglinear concentration-time curve. Only those data points judged to describe the terminal loglinear decline will be used in the regression.

*If data permit.

Actual PK sampling times will be used in derivation of PK parameters.

Table 9. Urine PF-00835231 PK Parameters Definitions for Part 1: SAD (24-h Continuous Infusion)

Parameter	Definition	Method of Determination
A _e	Amount of unchanged drug excreted in urine over 36 hours for QD dosing.	Sum of (urine volume x urine concentration) for each collection following dosing.
A _e %	Percent of dose excreted in urine as unchanged drug over the dosing interval.	100 × A _e /Dose.

Actual PK sampling times will be used in derivation of PK parameters.

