**Table 4. PK Parameters to be Summarized Descriptively for Part 1: SAD**

| Parameter  | Dose       | Summary Statistics   |
|--|------------|--|
| $C_{24}$   | All doses  | N, arithmetic mean, median, cv%, standard deviation, minimum, maximum, geometric mean and geometric cv%. |
| $AUC_{last}$ , $AUC_{inf}$ , $C_{24}$ , $C_{ss}$ , $C_{max}$ , CL and $V_{ss}$ | 500mg only | N, arithmetic mean, median, cv%, standard deviation, minimum, maximum, geometric mean and geometric cv%. |
| $t_{1/2}$  | 500mg only | N, arithmetic mean, median, cv%, standard deviation, minimum, maximum.                                   |

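### Setting below-quantification prodrug concentrations to zero conflicts with the geometric mean and geometric CV% that the SAP requires for C24 in Part 1 and C120 in Part 2

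*SAP*

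**What the plan says.** SAP Section 5.3 gives one rule for BLQ results in PK summaries and plots: "In all PK data presentations (except listings), concentrations below the limit of quantification (BLQ) will be set to zero". The same section lists what turns a concentration into a missing value: not done, no sample, a sampling-time deviation of concern, or an anomaly flag. BLQ is not on that list. SAP Section 6.2 refers the PK parameter summaries to Section 5.3 for missing values.

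Protocol Table 7 defines C24 as "Concentration at 24h (end of infusion in Part 1"), read directly from the data. Protocol Table 8 defines C120 in the same way for Part 2.

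SAP Table 2 ("Noncompartmental PK Parameters for Part 1: SAD") lists C24 for all doses and both analytes on the natural-log scale, without the asterisk that marks parameters reported only if data permit. The other Part 1 parameters are restricted to 500 mg. SAP Table 4 asks for these C24 statistics at all doses: "N, arithmetic mean, median, cv%, standard deviation, minimum, maximum, geometric mean and geometric cv"%. SAP Tables 3 and 5 do the same for C120 and its dose-normalised form, and SAP Section 6.2 plans a Part 2 plot of dose-normalised C120 and Css with a geometric mean for each dose.

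On doses, Protocol Section 4.3.2 records that "enrolment to Cohort 1 at 500 mg was stopped and a new cohort (Cohort 3) at 250 mg is open to enrolment". SAP Section 3.2 adds: "Urine PK was only planned to be collected in Part 1: SAD Cohort 2 and as this was not conducted".

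**The concern.** A geometric mean or geometric CV% needs the logarithm of every value, and zero has none. The plan therefore contains a stated data rule and a stated set of statistics that cannot both be followed once any C24 or C120 is BLQ.

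This is foreseeable for the prodrug. Protocol Section 2.2.2.1 reports that in healthy participants given 50 to 700 mg over 24 h, prodrug concentration fell before the infusion ended and "all plasma samples collected after the 16h post start of the infusion were BLQs of 40 ng/mL". C24 is sampled at exactly that late point. The active moiety is a lesser worry, since the same section says its concentration was sustained to the end of the infusion.

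At stake are two required cells for a secondary endpoint. They would be blank or zero, or filled by an unplanned rule. The last case matters most: software that discards undefined logarithms would summarise only the quantifiable patients, and the table would not say so.

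**Working it through.** The plan states no figure to reproduce here; no formal sample size calculation was performed and no inferential PK statistics are planned. The check has three steps.

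**1. What one zero does.** Geometric mean = exp(mean of ln x). Geometric CV% = 100 × √(exp(var of ln x) − 1). With one x = 0, ln x is undefined. The geometric CV% cannot be computed. The geometric mean is undefined on the SAP's log scale, or 0 if taken as the sixth root of the product of six values. That is 2 of the 9 statistics in SAP Table 4. If all values are zero, the arithmetic CV% (0/0) is lost as well.

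**2. How much the unstated choice matters.** Take five assumed quantifiable values of 55, 70, 85, 100 and 130 ng/mL plus one BLQ result, with a lower limit (LLQ) of 40 ng/mL:

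| Handling of the BLQ value | n | Geometric mean (ng/mL) | Geometric CV% | Median (ng/mL) |
|---|---|---|---|---|
| Zero (SAP 5.3) | 6 | 0 or undefined | not computable | 77.5 |
| LLQ/2 = 20 | 6 | 66.3 | 73.5 | 77.5 |
| LLQ = 40 | 6 | 74.4 | 44.3 | 77.5 |
| Dropped | 5 | 84.3 | 33.8 | 85.0 |

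The geometric CV% more than doubles between dropping the value and using half the limit (33.8 to 73.5). The median is the same for all three ways of keeping the patient in.

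**3. How often it could occur.** Protocol Section 9.2 gives 6 active participants per cohort. For a per-patient BLQ rate p, assumed because the documents give none, the chance of at least one BLQ value is 1 − (1 − p)^6:

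- p = 0.10: 1 − 0.9^6 = 0.469
- p = 0.25: 1 − 0.75^6 = 0.822
- p = 0.50: 1 − 0.5^6 = 0.984

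With only 4 active participants the figures are 1 − 0.9^4 = 0.344, 1 − 0.75^4 = 0.684 and 1 − 0.5^4 = 0.938. The healthy-participant data correspond to p = 1 after 16 h.

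**The case against.** The best defence is that Section 5.3 speaks of concentrations and suits the by-time concentration summary in SAP Section 6.2, which has no geometric statistics. PK parameters are derived only if data permit, so a non-quantifiable C24 could simply go unreported. This shows that the text can be read in more than one way, but it does not remove the problem. C24 and C120 are themselves concentrations, C24 carries no asterisk in Table 2, and Section 5.3 covers all PK presentations except listings. If BLQ values were left out, the table would describe quantifiable patients only (the last row of the table above), which the SAP does not state.

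The defence is right that the consequence is small. The arithmetic mean, SD, median, minimum and maximum survive; listings show BLQ results against the limit; the by-time summary counts values above it.

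Three stronger readings are tempting.

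- **That BLQ is near certain at 250 mg in patients.** The documents give no patient prodrug C24. Protocol Section 4.3.3 says exposures at 500 mg were roughly 2-fold (AUC24) to 3-fold (Cmax) "higher compared to those observed in healthy participants (C4611007) based on geometric mean values", but that concerns the active moiety and not a 24 h prodrug value. The 40 ng/mL limit is not stated for this study either.
- **That Cmax should be restored at 250 mg, or that prodrug exposure goes unchecked against the stopping limits.** Amendment 3 dropped parameters because reduced sampling could not support them, and the 6 h values are already summarised by time. Nothing in the documents tests C24 against a stopping limit.
- **That the zero rule was an oversight, because viral load and cytokines use the LLQ instead.** SAP version 2.0 revised Section 5.3, and a different rule for a different endpoint does not show neglect.

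**Conclusion.** The plan is wrong as written, and the point is minor. The zero rule and the required geometric statistics are incompatible for any dose group with at least one BLQ C24 or C120. That conclusion rests on the text and the definition of a logarithm alone. How often it will occur rests on assumption: the 47%, 82% and 98% figures illustrate BLQ rates of 10%, 25% and 50% in six independent participants and are not predictions.

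In Part 1 the exposed dose is chiefly 250 mg, where SAP Tables 2 and 4 provide no other prodrug parameter. The dose-normalised C24 named in Protocol Table 7 would carry the same zero. In Part 2 the conflict is the same for C120, but the documents do not say whether the late fall in prodrug recurs over a 120 h infusion. A reader might extend the point to Css. That goes too far: Css is an average over steady-state samples, so one BLQ input does not make it zero, and it is affected only if Css is itself zero.

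No hypothesis test or decision rule depends on these cells.

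**What to change.** Add to SAP Section 5.3, with a footnote to Tables 4 and 5: where any C24 or C120 value in a dose group is BLQ, or a Css is itself zero, report the number BLQ, the median and the range for that group. Compute no geometric mean or geometric CV% from zeros, or after dropping BLQ values without saying so. Apply the same rule to the Part 2 plot of dose-normalised C120 and Css, marking the affected group in place of a geometric mean. In the example above, the entry would read: 6 participants, 1 BLQ, median 77.5 ng/mL, range <40 to 130 ng/mL.

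The cost is a few sentences and a small programming change. It needs no new samples or parameters and leaves every safety limit alone. The price is that a group with any BLQ value has no geometric mean to set beside the other doses; the median serves instead.
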